7.2.4.3. Bacteriological response

Using the bacteriological response analysis set, the number of patients for each of the categories of bacteriological response will be counted, and the eradication rate defined in the formula below and its 95% CI will be calculated. Because a single patient can be infected and treated multiple times during the survey period, patients are counted in a treatment-based manner, i.e., they are counted as many times as the number of the treatments they received. If there is a case of multiple therapeutic treatments in a single patient, the eradication rate at the final observation point defined in the formula below, and its 95% CI will also be calculated. A similar analysis will be performed by reason of Mycobutin use.

$$\text{Eradication rate based on total number of cases (\%)} = \frac{(\text{Total number of eradicated cases})}{(\text{Total number of cases evaluated for bacteriological response except unknown})} \times 100$$

$$\text{Eradication rate at the final observation point (\%)} = \frac{(\text{Number of eradicated patients at the final observation point})}{(\text{Number of patients evaluated for bacteriological response except unknown at the final observation point})} \times 100$$

7.2.4.4. Subgroup Analysis

Subgroup analyses of the success rates of MAC prevention, clinical response rates (improvement rate), and eradication rates will be performed for each of the factors listed in Section 4.5.

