1.1. Study Design

As part of the HRD Joint Survey, this study includes HIV patients for whom Mycobutin is prescribed, including those captured in retrospective surveys. As far as possible, this part of the HRD joint Survey seeks to include all patients who receive Mycobutin at participating medical institutions. The indications and dosage and administration for Mycobutin, the survey periods, and the major investigation items are presented below.

- *Indications*

Susceptible strains: Mycobacteria susceptible to Mycobutin

Indications: Tuberculosis, nontuberculous mycobacteriosis including Mycobacterium avium complex (MAC) infection, and prevention of symptoms of disseminated MAC infection in HIV patients.

- *Dosage and Administration*

Tuberculosis:

For adults, an oral dose of rifabutin 150 mg to 300 mg is administered once daily.

For adults with multi-drug resistant tuberculosis, an oral dose of rifabutin 300 mg to 450 mg is administered once daily.

Treatment of nontuberculous mycobacteriosis including MAC infection:

For adults, an oral dose of rifabutin 300 mg is administered once daily.

Prevention of symptoms of disseminated MAC infection in HIV patients:

For adults, an oral dose of rifabutin 300 mg is administered once daily.

- *Survey Periods*

Tuberculosis and nontuberculous mycobacteriosis including MAC infection:

The survey will start on October 7, 2008, and the registration of patients will end at the end of the fiscal year after the 6th year.

Patient registration: October 7, 2008 - March 31, 2015

Prevention of the symptoms of disseminated MAC infection in HIV patients:

The survey will start on October 7, 2008, and the registration of patients will end at the end of the fiscal year after the 8th year.

Patient registration: October 7, 2008 - March 31, 2017

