4. ANALYSIS SETS

4.1. Safety Analysis Set

The safety analysis set consists of the patients who meet the inclusion criteria for this study and are confirmed to have received at least one dose of Mycobutin. However patients who have received treatment with Mycobutin before marketing (those who discontinued or completed their treatment with Mycobutin before the marketing of Mycobutin[®] 150mg Capsules) will be excluded from the safety analysis set.

4.2. (Preventive) Effectiveness Analysis Set

Among the patients in the safety analysis set, those who received Mycobutin for the prevention of MAC infection and underwent an effectiveness evaluation (determination of whether an onset of MAC infection is observed or not) comprise the (preventive) effectiveness analysis set.

4.3. (Therapeutic) Effectiveness Analysis Set

Among the patients in the safety analysis set, those who underwent at least one post-treatment effectiveness evaluation (determination of bacteriological response or clinical efficacy at the end of the observation period) comprise the (therapeutic) effectiveness analysis set.

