- Baseline CD4 count (cells/mm³) [≥0 to <100, ≥100 to <200, ≥200 to <350, ≥350 to <500, ≥500]
- Centers for Disease Control and Prevention (CDC) classification [A, B, C, P-0, P-1, P-2]

Subgroup analyses of effectiveness will also be performed for the following other factors:

- Maximum daily dose [<150 mg, 150 mg, 300 mg, 450 mg, >450 mg]
- Mean daily dose [<150 mg, 150 mg, >150 mg to <300 mg, 300 mg, >300 mg to <450 mg, 450 mg, >450 mg]
- Duration of one prophylactic or therapeutic treatment [≤1 week, >1 week to ≤2 weeks, >2 weeks to ≤4 weeks, >4 weeks to ≤8 weeks, >8 weeks to ≤12 weeks, >12 weeks to ≤24 weeks, >24 weeks to ≤36 weeks, >36 weeks to ≤1 year, >1 year]
- Concomitant medications (anti-MAC drugs) [absent, present]
- Concomitant use of SMX/TMP [absent, present]

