8. LISTINGS

The following listings will be prepared (Tabulated summaries that are intended to be included in the study report are indicated as “for intext”):

- Listing for registered patients and patients for whom the case report form was collected
- Listing for the decision of eligibility
- Listing of patients of all registered patients
- Listing of patients in the safety analysis set
- Listing of patients in the (preventive) effectiveness analysis set
- Listing of patients in the (therapeutic) effectiveness analysis set
- Listing of patients in the bacteriological response analysis set
- Listing of patients with adverse events
- Listing of patients with adverse drug reactions
- Listing of patients with adverse drug reactions among patients excluded from the safety analysis set
- Listing of patients with serious adverse drug reactions (for intext)
- Listing of patients with SAEs
- Listing of patients with adverse drug reactions among patients with hepatic dysfunction (for intext)
- Listing of patients with adverse drug reactions among patients with renal dysfunction (for intext)
- Listing of patients with adverse drug reactions among elderly patients
- Listing of patients with adverse drug reactions after long-term (>1 year) treatment
- Listing of patients with adverse drug reactions due to overdose
- Listing of events falling under major investigation items
- Listing of patients with adverse drug reactions falling under major investigation items (for intext)
- Listing of the status of administration of Mycobutin
- Listing of concomitant medications used
- Listing of bacteriological tests
- Listing of patients who concomitantly used SMX/TMP
- Listing of concomitant medications used for NTM infections (including MAC infection) and tuberculosis
- Listing of the changes in HIV-RNA copy number, CD4 count, and body weight for individual patients

In addition, the following tables that correspond to the Appendix Forms required for the periodic safety update report will be prepared:

- Appendix Form 3 (Listing of overview of patients)
- Appendix Form 2 (Listing of occurrence of adverse drug reaction and infections)
- Appendix Form 10 (Appendix Form 2-2) (Listing of occurrence of SAEs)

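### The effectiveness tables by dose and by anti-MAC co-medication pool tuberculosis, MAC and other NTM, so a difference between infections can appear as a dose or co-medication effect

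*SAP*

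**What the plan says.** SAP 7.2.4.4 states that subgroup analyses of the three effectiveness rates "will be performed for each of the factors listed in Section 4.5". It mentions no stratification or adjustment. Among the effectiveness factors in SAP 4.5 are "Maximum daily dose [<150 mg, 150 mg, 300 mg, 450 mg, >450 mg", mean daily dose, and "Concomitant medications (anti-MAC drugs) [absent, present". Reason for use is not on that list.

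The therapeutic effectiveness set (SAP 4.3) takes "those who underwent at least one post-treatment effectiveness evaluation" and is not divided by infection. The clinical response and eradication formulas in 7.2.4.2 and 7.2.4.3 also run over all infections together.

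SAP 1.1 gives the labelled dose by infection:
- Tuberculosis: "For adults, an oral dose of rifabutin 150 mg to 300 mg is administered once daily".
- Multi-drug resistant tuberculosis: "For adults with multi-drug resistant tuberculosis, an oral dose of rifabutin 300 mg to 450 mg is administered once daily".
- NTM including MAC: "For adults, an oral dose of rifabutin 300 mg is administered once daily".

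Reason for use appears in three places. It is a background tabulation (7.2.2), a factor for adverse drug reactions (7.2.3.4) and a breakdown of the overall eradication rate (7.2.4.3). It is not applied to clinical response and is not crossed with dose or co-medication. The only covariate in SAP 5.4 is for safety.

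**The concern.** A factor table is informative about the factor only if the groups being compared are otherwise similar. Here the dose groups differ in which infection they contain, by the label itself. The co-medication factor is named after one of the infections, so its two groups probably differ in the same way. If tuberculosis, MAC and other NTM respond at different rates, the rows of a pooled table will differ even when neither dose nor co-medication does anything.

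Identifying factors that affect effectiveness is a stated objective (Protocol 1, SAP 1.2). Protocol 1 also says that the results support reexamination and are fed back to healthcare professionals every year. A reader of the planned clinical response tables could not tell the two explanations apart, because no by-infection clinical response rate is planned.

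**Working it through.** The documents state no response rate, infection mix, sample size or pattern of co-medication, so there is no planned figure to reproduce. The check has two parts.

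**1. Labelled dose set against the dose categories (SAP 1.1 and 4.5)**

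| Reason for treatment | 150 mg | 300 mg | 450 mg |
|---|---|---|---|
| Tuberculosis | yes | yes | no |
| Multi-drug resistant tuberculosis | no | yes | yes |
| NTM including MAC | no | yes | no |

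On labelled use, the 150 mg and 450 mg rows contain only tuberculosis. The 300 mg row mixes all infections.

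**2. Size of the false gap when dose has no effect within any infection**

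Assumptions, none of them from the documents:
- s = tuberculosis share of courses: 20%, 40% or 60%.
- a = share of tuberculosis courses at 150 mg: 50%, the rest at 300 mg. The 450 mg row is left out.
- m = share of MAC/NTM courses at 150 mg: 0 on labelled dosing, or higher.
- pT and pM = response in tuberculosis and in MAC/NTM.

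Formulas:
- Rate at 150 mg = [s·a·pT + (1−s)·m·pM] / [s·a + (1−s)·m]
- Rate at 300 mg = [s·(1−a)·pT + (1−s)·(1−m)·pM] / [s·(1−a) + (1−s)·(1−m)]

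Worked case, s = 40%, m = 0, pT = 80%, pM = 50%:
- 150 mg: (0.4 × 0.5 × 0.8) / (0.4 × 0.5) = 80.0%
- 300 mg: (0.16 + 0.30) / (0.20 + 0.60) = 0.46 / 0.80 = 57.5%
- Gap: 22.5 points, with no dose effect present.

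Gap, 150 mg minus 300 mg, in percentage points:

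| Response, tuberculosis / MAC-NTM | MAC/NTM at 150 mg | s = 20% | s = 40% | s = 60% |
|---|---|---|---|---|
| 80% / 50% | 0% | 26.7 | 22.5 | 17.1 |
| 80% / 50% | 10% | 13.0 | 15.0 | 12.8 |
| 80% / 50% | 30% | 4.3 | 6.1 | 5.9 |
| 80% / 50% | 50% | 0 | 0 | 0 |
| 80% / 70% | 0% | 8.9 | 7.5 | 5.7 |
| 60% / 80% | 0% | −17.8 | −15.0 | −11.4 |
| 80% / 80% | any | 0 | 0 | 0 |

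The gap vanishes if response is the same in all infections, or if dose is unrelated to infection (m = a = 50%). Its sign follows whichever infection responds better.

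The same formulas apply to anti-MAC drugs, with use shares in place of dose shares. If use were 90% in MAC/NTM and 10% in tuberculosis, users would look worse by 20 to 24 points at 80%/50% and better by 13 to 16 points at 60%/80%. Those use shares are assumed only to show the mechanism.

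**After stratifying by reason for use**

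In every scenario the within-infection difference is zero: 80% against 80% in tuberculosis, and 50% against 50% in MAC/NTM where both doses occur. A Mantel-Haenszel difference is a weighted average of these, so it is also zero.

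**The case against.** The strongest reply has several parts.

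- **The analyses are exploratory.** SAP 3.1 treats p-values as descriptive, 7.2.4.4 names no test, and 7.2.4.5 allows extra analyses. This lowers the stakes. It does not take the infection mix out of the tables, and it does not commit anyone to the stratified version.
- **Labelled dosing is not observed dosing.** This stands. The survey describes actual use, all infections share 300 mg, and the categories below 150 mg and above 450 mg foresee other doses. A reader might infer that dose is fully fixed by infection; the documents support only a strong link under the label. The table shows how quickly the gap shrinks as that link weakens.
- **The anti-MAC link is an inference.** This also stands. A reader might infer that the factor excludes the companion drugs used for tuberculosis, so that tuberculosis courses fall under absent. The documents neither define the drug class nor give its use by infection.
- **Splitting by reason for use does not separate resistant from susceptible tuberculosis.** Correct. SAP 7.2.2 has a single tuberculosis category. A reader might expect the split to correct a poor result at 450 mg that is really due to resistance; it would not. On labelled dosing, moreover, MAC and other NTM have one populated dose row each, so any dose comparison comes from tuberculosis alone.
- **Part of this is already handled.** Prevention has its own analysis set and success rate (4.2, 7.2.4.1), so it is not affected. Eradication is reported by reason for use overall, which lets a reader see infection differences for that endpoint only.

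A reader might also extend the point to the safety tables. SAP 7.2.3.4 already tabulates adverse drug reactions by reason for use, and nothing worked out here bears on safety.

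**Conclusion.** The point holds for the clinical response and eradication rates. As planned, the tables by maximum dose, mean dose and anti-MAC co-medication can report a difference between infections as a factor effect, and no required analysis separates the two.

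This rests on two conditions: response differs by infection, and dose or co-medication is related to infection in the patients observed. For dose, the label supports the second condition; for anti-MAC drugs it is only presumed. The documents do not settle the first, so neither the size nor the direction of the distortion can be stated. The figure of 17 to 27 points is an illustration for 80% against 50% response on labelled dosing. It falls to 4 to 6 points with 30% of MAC/NTM courses at 150 mg, and to zero with equal response.

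The SAP should be amended. The exploratory status limits the harm, but these tables are the plan's answer to a stated objective. The point concerns analysis only and implies nothing about which dose is right.

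**What to change.** 1. In SAP 7.2.4.4, report maximum dose, mean dose and anti-MAC co-medication for clinical response and eradication within each reason for use. Where cells are small, use tuberculosis against MAC/NTM. Alternatively, give an estimate stratified by reason, such as Mantel-Haenszel.
2. In SAP 7.2.4.2, add the clinical response rate by reason for use, matching what 7.2.4.3 already does for eradication.
3. Within tuberculosis, split by multi-drug resistance if the data allow. The documents do not say whether resistance is recorded in usable form. If it is not, state in the report that dose and resistance cannot be separated, and draw no dose conclusion.

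Reason for use and dose are already tabulated under 7.2.2, and Section 8 already plans a "Listing of concomitant medications used for NTM infections (including MAC infection) and tuberculosis", so the first two changes need SAP wording and tables, not new data. The cost is smaller cells, some possibly empty, since on labelled dosing MAC and other NTM occupy only the 300 mg row.

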7.2.4.5. Exploratory Analysis

Additional analyses may be performed as necessary. The results of an exploratory analysis will be reported only when they result in an important interpretation.

8. LISTINGS

The following listings will be prepared (Tabulated summaries that are intended to be included in the study report are indicated as “for intext”):

- Listing for registered patients and patients for whom the case report form was collected
- Listing for the decision of eligibility
- Listing of patients of all registered patients
- Listing of patients in the safety analysis set
- Listing of patients in the (preventive) effectiveness analysis set
- Listing of patients in the (therapeutic) effectiveness analysis set
- Listing of patients in the bacteriological response analysis set
- Listing of patients with adverse events
- Listing of patients with adverse drug reactions
- Listing of patients with adverse drug reactions among patients excluded from the safety analysis set
- Listing of patients with serious adverse drug reactions (for intext)
- Listing of patients with SAEs
- Listing of patients with adverse drug reactions among patients with hepatic dysfunction (for intext)
- Listing of patients with adverse drug reactions among patients with renal dysfunction (for intext)
- Listing of patients with adverse drug reactions among elderly patients
- Listing of patients with adverse drug reactions after long-term (>1 year) treatment
- Listing of patients with adverse drug reactions due to overdose
- Listing of events falling under major investigation items
- Listing of patients with adverse drug reactions falling under major investigation items (for intext)
- Listing of the status of administration of Mycobutin
- Listing of concomitant medications used
- Listing of bacteriological tests
- Listing of patients who concomitantly used SMX/TMP
- Listing of concomitant medications used for NTM infections (including MAC infection) and tuberculosis
- Listing of the changes in HIV-RNA copy number, CD4 count, and body weight for individual patients

In addition, the following tables that correspond to the Appendix Forms required for the periodic safety update report will be prepared:

- Appendix Form 3 (Listing of overview of patients)
- Appendix Form 2 (Listing of occurrence of adverse drug reaction and infections)
- Appendix Form 10 (Appendix Form 2-2) (Listing of occurrence of SAEs)

10. APPENDIX

10.1. Appendix 1: Details of Data Collection

A1.1 Definition of visits

Visit	Endpoints	Definition [Allowance]
At start of treatment	HIV-RNA, CD4, CDC category, body weight, bacteriological tests	Data obtained before and on the day of the first dose (treatment start) of this survey. If there are multiple data, select data on the day closest to the first dose day of this survey.
At end of observation	Effectiveness endpoints	Data obtained on the day of the last dose of this survey or before and after the day. If there are multiple data, select data on the day closest to the last dose day of this survey.
